## APPENDIX I INSTRUCTIONS FOR USE OF M&S NEAR VISUAL ACUITY CHART

Near visual acuity will be measured using the M&S near charts designed for 40 cm. The M&S system background luminance is set to 85 cd/m^2 (range of 80 – 110 cd/m^2 is acceptable). Room lighting is to be set at a level lower than the illumination from the laptop screen. Ambient lighting should be mesopic (30-50 lux) to maximize pupil size. No surface (including reflective surfaces) within the subject's field of vision should exceed the chart background in luminance.

The M&S system should be placed precisely at 40 cm from the subject for testing near visual acuities.

Subjects should be reminded prior to testing that squinting is not allowed. Trial frames should be used for visual acuity testing with careful observation by the testing technician to ensure the subject is not squinting. If squinting is observed, the subject is to be reminded by the testing technician not to squint.

Monocular testing will be completed for each measurement before binocular testing is done. All subjects should be tested monocularly and binocularly, uncorrected and with distance correction in place. Visual acuity measurements are based on the total number of correctly read letters. Subjects should be persuaded to read the smallest letters possible even if they have to guess. Record the total number of letters read correctly for each near test on the case report form.

All subjects will be tested both uncorrected and best corrected, monocularly and binocularly. To test subjects monocularly, occlude the fellow eye in the phoropter or with an occluder (if trial lenses are used) and encourage subjects to read the smallest letters possible even if they have to guess. Visual acuity measurements are based on the total number of correctly read letters. Subjects should be instructed to start with the smallest line where they can read all of the letters. If they miss any letters, go up a line until they are able to read all the letters on a line, then continue to read each subsequently smaller line. The subject should be encouraged to read as many letters possible, even if they have to guess. Testing may be stopped when it is evident that no further readings can be made. Record the total number of letters read correctly on the chart. This will be displayed on the laptop screen along with the logMAR and Snellen acuity. Then begin testing for the fellow eye and repeat with both eyes together for binocular testing.

## APPENDIX J INSTRUCTIONS FOR DEFOCUS CURVE TESTING USING THE M&S SYSTEM

All defocus curve testing is to be performed using the M & S Technologies CTS-1000 Smart System in logMAR format (100% contrast) at a distance of 4.0 meters and calibrated to a photopic luminance of 85 cd/m^2 (range 80-110 cd/m^2 is acceptable).

The M&S system background luminance is set to 85 cd/m^2 (range of 80 – 110 cd/m^2 is acceptable). Room lighting is to be set at a level lower than the illumination from the laptop. Ambient lighting should be mesopic (30-50 lux) to maximize pupil size. No surface (including reflective surfaces) within the subject's field of vision should exceed the laptop in luminance.

Subjects should be reminded prior to testing that squinting is not allowed. During defocus curve testing, trial frames will be used to allow observation by the testing technician to ensure the subject is not squinting. If squinting is observed, the subject is to be reminded by the testing technician not to squint.

This test is to be done on all subjects.

Monocular Defocus Curve Testing: Starting with the subject's distance correction in place, begin testing by occluding the left eye and defocusing the image by +2.00 D over the manifest distance correction in the right eye. Subjects should be instructed to start with the smallest line where they can read all of the letters. If they miss any letters, go up a line until they are able to read all the letters on a line, then continue to read each subsequently smaller line. The subject should be encouraged to read as many letters possible, even if they have to guess. Testing may be stopped when it is evident that no further readings can be made. Record the total number of letters read correctly on the chart. This will be displayed on the laptop screen along with the logMAR and Snellen acuity. Then reduce the amount of defocus in the right eye by -0.50 D, to +1.50 D, and repeat the acuity test, recording the visual acuity LogMAR value. Continue to change the defocus in -0.50 D increments in the right eye, repeating the test and documenting the visual acuity LogMAR value at each level of defocus. Continue to change the defocus to -3.00 D over the subject's distance correction.

## APPENDIX K INSTRUCTIONS FOR PUPIL SIZE MEASUREMENTS

### PHOTOPIC PUPIL SIZE:

Pupil size for each eye should be measured under photopic ambient lighting conditions of 480 – 520 lux. Photopic pupil size should be measured using the NeurOptics pupillometer. To measure distance pupil size, have the subject focus the eye not being measured without glasses at a distance target (logMAR 0.4, unless this cannot be seen uncorrected) and record the pupil size measurements. To measure near pupil size, have the subject focus the eye not being measured without glasses at a near target at 40 cm (logMAR 0.4, unless this cannot be seen uncorrected) and record the pupil size measurements.

### MESOPIC PUPIL SIZE:

Pupil size for each eye should be measured under mesopic ambient lighting conditions of 30-50 lux. For mesopic measurements, the NeurOptics pupillometer should be used. To measure distance pupil size, have the subject focus the eye not being measured without glasses at a distance target (logMAR 0.4, unless this cannot be seen uncorrected) and record the pupil size measurements. To measure near pupil size, have the subject focus the eye not being measured without glasses at a near target at 40 cm (logMAR 0.4, unless this cannot be seen uncorrected) and record the pupil size measurements.

## APPENDIX L INSTRUCTIONS FOR KERATOMETRY

Keratometry must be performed prior to dilation and any contact with the cornea (e.g., tonometry or pachymetry) as follows:

1. Measure keratometry using the iDesign System AND an auto or manual keratometer using the same method at each required visit, e.g., if auto keratometry was recorded at the preoperative exam, all keratometry readings postoperatively should be auto K's.
2. **Do not use “sim K”s from the corneal topography unit.**
3. Always record the flat meridian (smaller number, e.g., 42.25) as K1. Record the steeper meridian (larger number, e.g., 43.00) as K2 along with the corresponding axis (e.g., 42.25 / 43.00 x 165).
4. Record spherical corneas by placing the corneal curvature values in both K1 and K2 and marking axes 180 attached to K2 (e.g., 44.00 / 44.00 x 180). **Spherical Ks will not be accepted with axes other than 180 (do not use 0).**

## APPENDIX M SLIT-LAMP EXAM RATINGS

### A. Corneal Clarity

Below is the grading scale to be used for corneal clarity.

Grade	Description
0.0	Clear
0.5	Faint / trace haze
1.0	Mild haze, not affecting refraction
2.0	Moderate haze, refraction possible
3.0	Haze / prevents refraction, AC visible
4.0	Haze / AC not visible

## APPENDIX N      CLINICAL WORKFLOW & LASIK SURGICAL PROCEDURE

### Clinical Workflow:

1. Patients will be measured on the iDesign 1.2 system.
2. The same iDesign system will be used for all measurements (in the event there is more than one iDesign in the center).
3. Preoperatively, iDesign exams will be acquired until an exam is selected for treatment. Postoperatively, a single iDesign exam will be acquired.
4. The iDesign 1.2 system database will be exported using the iDesign Export functionality on the Utilities Tab for all exams of the patient(s) being treated.
5. The exported patient database will be imported into the iDesign 1.3-PRESBY software (modified for this study) on the AMO provided laptop.
6. The treatments for the control and test eyes will be programmed and designed on the iDesign 1.3 PRESBY software. No Physician Adjustment or Percentage Nomogram adjustments will be used.
7. The treatments for the test eye (non-dominant eye) with presbyopia option turned **ON** and the control eye (dominant eye) with presbyopia option turned **OFF** will be calculated on iDesign 1.3-PRESBY software for the selected exams.
8. Treatments will be saved to USB and transferred to the STAR S4 IR laser.
9. Treatments will be executed on the STAR S4 IR laser.

### LASIK Surgical Procedure:

The following steps represent a typical LASIK surgical procedure and should be used as a standard model. Both eyes may be treated on the same day provided that treatment of the first eye is without an adverse event or clinically significant surgical complication. Any epithelial defect on the flap will preclude treatment of the fellow eye. However, placement of a bandage contact lens is at the discretion of the investigator does not preclude treatment of the fellow eye at the same time.

1. At the physician's discretion, administer a systemic medication (e.g., analgesic or sedative).
2. Apply topical ophthalmic anesthetic agent to the operative eye(s).
3. With the subject at the slit lamp and the eye anesthetized, ask the subject to fixate with both eyes on the letter chart at the end of the room. Use a sterile marking pen to mark the limbus at 3 and 9 o'clock. Marking may be facilitated by drying the area to be marked first with a sterile sponge. After marking the eye, ask the subject to close the eyes and keep the eyes closed until they are brought into the laser room.

4. Create a flap with the IntraLase® Femtosecond Laser.
5. Position the subject on the operating chair of the S4 IR Excimer Laser System.
6. Perform a lid scrub with a topical surgical disinfectant.
7. Shield the fellow eye and prepare the operative eye for the procedure.
8. Position chair underneath laser and lock. Turn on the fiducial line and align the subject. Make the adjustments to the surgeon chair and microscope to allow proper positioning and focus.
9. Instill topical ophthalmic anesthetic agent to the operative eye.
10. Place a lid speculum into position.
11. Activate the recording device(s) (e.g., DVD recorder), and begin video acquisition of the subject's procedure.
12. Align the eye with the appropriate hash marks on the reticle by moving the head prior to vacuum pillow deflation.
  
13. Remove fluid from the fornices with an ophthalmic surgical sponge.
14. Displace the flap toward the hinge.
15. Perform intra-operative pachymetry with an ultrasonic pachymeter if the estimated residual stromal bed depth is ≤ 320 microns.

**NOTE: If the estimated residual stromal bed thickness is < 250 microns, the investigational treatment must not be performed.**
16. Ensure magnification on the operating microscope is 1.6X. Ensure the subject's pupil is centered in the reticle as the subject is fixating on the fixation LED. Focus on the anterior stromal surface.
17. Remind patient to fixate on flashing LED, then activate ActiveTrak and Iris Registration on the STAR S4 IR™ Excimer Laser System.
18. Confirm proper placement of OIB (outer iris boundary).
19. After ensuring that the reticle is centered over the subject's pupil and the subject is viewing the fixation light, fully depress the foot pedal to perform the laser treatment. If necessary, stop the laser and dry the cornea if there is fluid accumulation.
20. Replace the flap and irrigate as necessary. Assure flap is re-adhered.
21. Apply topical ophthalmic medications to the cornea and move the subject away from the laser.
22. Note the intended flap thickness setting used, the treatment time, whether the eye tracker lost track of the eye at any time during the procedure, and the environmental conditions (temperature and humidity).
23. Print the S4 IR Operative Report.
24. Note any adverse events or complications that occurred during treatment. Report any adverse events to the Sponsor.

**APPENDIX O            EXAMPLE PATIENT REPORTED OUTCOMES  
QUESTIONNAIRE**

**PRVSQ-LASIK/PRK**

**This questionnaire asks about your visual symptoms  
OVER THE LAST 7 DAYS.**

**For ALL questions, please mark an  in the box or boxes  
that best describe your answer.**

The next few questions ask about halos.

**Halos** are bright circles or rings that appear around a source of light, such as oncoming car headlights.

Q1a. Over the last 7 days, how often did you experience halos?

- Never (**go to question Q2a**)
- Rarely
- Sometimes
- Often
- Always

If you experienced halos in the last 7 days, please answer the following questions.

Q1b. Did you experience halos... **Check all that apply.**

- When **not** wearing corrective glasses or contacts
- When wearing corrective glasses or contacts
- When wearing any type of sunglasses

Q1c. Did you experience halos... **Check all that apply.**

- During the day
- During the night
- During dawn or dusk

Q1d. Did you experience halos... **Check all that apply.**

- When driving during the day
- When driving at night
- When driving at dawn or dusk

Q1e. Overall, how much were you bothered by halos?

- Not at all bothered
- Slightly bothered
- Moderately bothered
- Very bothered
- Extremely bothered

Q1f. Is there anything you have a lot of difficulty with, or do not do, because of halos?

- No
- Yes. If Yes, please describe:

The next few questions ask about glare.

**Glare** is reflected light making it difficult to see. **Glare** may occur as light reflecting off of water, a window or pavement.

Q2a. Over the last 7 days, how often did you experience glare?

- Never (**go to question Q3a**)
- Rarely
- Sometimes
- Often
- Always

If you experienced glare in the last 7 days, please answer the following questions.

Q2b. Did you experience glare... ***Check all that apply.***

- When **not** wearing corrective glasses or contacts
- When wearing corrective glasses or contacts
- When wearing any type of sunglasses

Q2c. Did you experience glare... ***Check all that apply.***

- During the day
- During the night
- During dawn or dusk

Q2d. Did you experience glare... ***Check all that apply.***

- When driving during the day
- When driving at night
- When driving at dawn or dusk

Q2e. Overall, how much were you bothered by glare?

- Not at all bothered
- Slightly bothered
- Moderately bothered
- Very bothered
- Extremely bothered

Q2f. Is there anything you have a lot of difficulty with, or do not do, because of glare?

- No
- Yes. If Yes, please describe:

The next few questions ask about starbursts.

**Starbursts** are lines or rays that appear to surround a source of light, such as oncoming car headlights.

Q3a. Over the last 7 days, how often did you experience starbursts?

- Never (**go to question Q4a**)
- Rarely
- Sometimes
- Often
- Always

If you experienced starbursts in the last 7 days, please answer the following questions.

Q3b. Did you experience starbursts... ***Check all that apply.***

- When **not** wearing corrective glasses or contacts
- When wearing corrective glasses or contacts
- When wearing any type of sunglasses

Q3c. Did you experience starbursts... ***Check all that apply.***

- During the day
- During the night
- During dawn or dusk

Q3d. Did you experience starbursts... ***Check all that apply.***

- When driving during the day
- When driving at night
- When driving at dawn or dusk

Q3e. Overall, how much were you bothered by starbursts?

- Not at all bothered
- Slightly bothered
- Moderately bothered
- Very bothered
- Extremely bothered

Q3f. Is there anything you have a lot of difficulty with, or do not do, because of starbursts?

- No
- Yes. If Yes, please describe:

The next few questions ask you about sensitivity to light.

**Sensitivity to light** is a decreased ability to tolerate light, such as sunlight, fluorescent light or incandescent light. Such sensitivity can cause discomfort resulting in a need to squint, close or shade your eyes.

Q4a. Over the last 7 days, how often did you experience sensitivity to light?

- Never (**go to question Q5a**)
- Rarely
- Sometimes
- Often
- Always

If you experienced sensitivity to light in the last 7 days, please answer the following questions.

Q4b. Did you experience sensitivity to light... ***Check all that apply.***

- When **not** wearing corrective glasses or contacts
- When wearing corrective glasses or contacts
- When wearing any type of sunglasses

Q4c. Did you experience sensitivity to light... ***Check all that apply.***

- During the day
- During the night
- During dawn or dusk

Q4d. Did you experience sensitivity to light... ***Check all that apply.***

- When driving during the day
- When driving at night
- When driving at dawn or dusk

Q4e. Overall, how much were you bothered by sensitivity to light?

- Not at all bothered
- Slightly bothered
- Moderately bothered
- Very bothered
- Extremely bothered

Q4f. Is there anything you have a lot of difficulty with, or do not do, because of sensitivity to light?

- No
- Yes. If Yes, please describe:

The next few questions ask you about multiple or double vision.

**Multiple or double vision** is when objects appear as separate or overlapping images.

Q5a. Over the last 7 days, how often did you experience multiple or double vision?

- Never (**go to question 6a**)
- Rarely
- Sometimes
- Often
- Always

If you experienced multiple or double vision in the last 7 days, please answer the following questions.

Q5b. Did you experience multiple or double vision... **Check all that apply.**

- When **not** wearing corrective glasses or contacts
- When wearing corrective glasses or contacts
- When wearing any type of sunglasses

Q5c. Did you experience multiple or double vision... **Check all that apply.**

- During the day
- During the night
- During dawn or dusk

Q5d. Did you experience multiple or double vision... **Check all that apply.**

- When driving during the day
- When driving at night
- When driving at dawn or dusk

Q5e. Overall, how much were you bothered by multiple or double vision?

- Not at all bothered
- Slightly bothered
- Moderately bothered
- Very bothered
- Extremely bothered

Q5f. Is there anything you have a lot of difficulty with, or do not do, because of multiple or double vision?

- No
- Yes. If Yes, please describe:

The next few questions ask you about fluctuating vision.

**Fluctuating vision** is changes in how clearly you see throughout the day.

Q6a. Over the last 7 days, how often did you experience fluctuating vision?

- Never (**go to question 7**)
- Rarely
- Sometimes
- Often
- Always

If you experienced fluctuating vision in the last 7 days, please answer the following questions.

Q6b. Did you experience fluctuating vision... ***Check all that apply.***

- When **not** wearing corrective glasses or contacts
- When wearing corrective glasses or contacts
- When wearing any type of sunglasses

Q6c. Did you experience fluctuating vision... ***Check all that apply.***

- During the day
- During the night
- During dawn or dusk

Q6d. Did you experience fluctuating vision... ***Check all that apply.***

- When driving during the day
- When driving at night
- When driving at dawn or dusk

Q6e. Overall, how much were you bothered by fluctuating vision?

- Not at all bothered
- Slightly bothered
- Moderately bothered
- Very bothered
- Extremely bothered

Q6f. Is there anything you have a lot of difficulty with, or do not do, because of fluctuating vision?

- No
- Yes. If Yes, please describe:

The next question asks about any other visual symptoms.

Q7. Over the last 7 days, have you experienced any other **visual symptoms** not described above?

No

Yes. If Yes, please describe:

---

---

---

---

---

---

## APPENDIX P CONTACT LENS STUDY PROCEDURES

### Study Materials

Subjects will wear a single vision distance contact lens in their dominant eye and a multifocal contact lens in their non-dominant eye. Details of the lenses are shown in the Table below. Subjects with astigmatism  $\geq 0.75\text{D}$  in the dominant eye and  $\geq 1.25\text{ D}$  in the non-dominant eye must be fit with a toric lens in their respective eye. It is recommended that subjects wear their lenses daily for a minimum of 10 hours.

TABLE 2: Study Lenses

	PROCLEAR SPHERE (DOMINANT EYE)	PROCLEAR TORIC (DOMINANT EYE)	PROCLEAR MULTIFOCAL D LENS (NON-DOMINANT EYE)	PROCLEAR MULTIFOCAL TORIC D LENS (NON-DOMINANT EYE)
Base Curve (mm)	8.6	8.8	8.7	8.8
Lens Diameter (mm)	14.2	14.4	14.4	14.4
Sphere (D)	-1.00 to -6.00 (0.25 D steps)	-1.00 to -6.00 (0.25 D steps)	-1.00 to -6.00 (0.25 D steps)	-1.00 to -6.00 (0.25 D steps)
Cylinder (D)	N/A	-0.75 to -4.75 (0.50 D steps)	N/A	-0.75 to -4.75 (0.50 D steps)
Add (D)	None	None	+1.50D	+1.50D

### Contact Lens Care

Subjects will be provided with contact lenses as recommended above, and instructed to use a contact lens solution per the instruction of the investigator.

### Storage of Study Lenses

The study materials must be stored in a secure area and administered only by authorized study personnel. It is recommended that all lenses be stored at controlled room temperature (59-86 F).

### Ordering and Accountability of Study Materials

The contact lenses will be ordered by the investigator. The contact lens solutions will be provided by the clinical site.

### **Disposal of Consumables**

Study lenses worn by the subject will be disposed of by either the subject or by the investigator.

**APPENDIX Q PATIENT QUESTIONNAIRE – CONTACT LENS STUDY**

Subject Name \_\_\_\_\_ Visit Date \_\_\_\_\_

**1. Please answer the following questions regarding your visual satisfaction and comfort while performing daily activities during the contact lens study.**

	Very Satisfied	Satisfied	Somewhat Satisfied	Somewhat Dissatisfied	Very Dissatisfied	Not Applicable
Driving during daylight	5	4	3	2	1	0
Driving at night	5	4	3	2	1	0
Working on a computer	5	4	3	2	1	0

**2. Please rate your overall experience with the contact lens study over the last 7 days.**

Very Satisfied	Satisfied	Somewhat Satisfied	Somewhat Dissatisfied	Very Dissatisfied	Not Applicable
5	4	3	2	1	0

Comments: \_\_\_\_\_

Investigator Signature \_\_\_\_\_

## APPENDIX R OCULAR DOMINANCE - DOLMAN TEST

Hole-in-the-card test

1. Instruct the subject to hold a card with a hole in the middle with both hands at arm's length centered in front of themselves.
2. With both eyes open, view the examiner's nose standing on the other side of the room through the center hole.
3. The examiner is to look directly at the subject, and confirm which eye the subject is using for viewing i.e. the dominant eye.

## APPENDIX S ADVERSE EVENT AND COMPLAINT REPORTING INSTRUCTIONS

All adverse events and complaints related to using AMO products must be reported to AMO.

### ALL ADVERSE EVENTS AND COMPLAINTS:

For events that are not considered serious or related to the study device:

1. Record the event and/or complaint on the case report form that corresponds to the visit during which awareness of the event occurred. Additionally, a complaint may be reported via a telephone call to AMO.
2. Ensure the data are submitted to AMO electronically within a timely manner.

### SERIOUS ADVERSE EVENTS OR DEVICE DEFICIENCIES THAT MAY HAVE LED TO A SERIOUS EVENT

In the event of a serious event (i.e., life- or sight-threatening incident) whether or not related to the device, or a device deficiency that may have led to a serious event, the investigator shall:

1. Notify AMO immediately (no more than 48 hours after learning of the event) as follows:
  - a. Contact the following AMO personnel by phone:  
  

  - b. Complete a Detailed Adverse Event Form and submit electronically to AMO

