#### **Serious Adverse Event (SAE)**

An adverse event is considered serious (following ISO 14155) if it is an untoward occurrence which may or may not be related to use of the study device that

- is sight- or life-threatening,
- results in death,
- requires inpatient hospitalization or prolongation of hospitalization (a planned hospitalization for a pre-existing condition is not considered a serious adverse event),
- results in permanent impairment of a body structure or body function,
- necessitates medical or surgical intervention to prevent permanent impairment to a body structure or function, or
- results in fetal distress, fetal death or a congenital abnormality or birth defect

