### **11.3 ADVERSE EVENT AND COMPLAINT REPORTING REQUIREMENTS**

All adverse events and any complaint encountered using any AMO product, regardless of severity and whether or not attributed to the study device(s), are to be reported to AMO and recorded on the case report form corresponding to the visit during which awareness of the event occurred. Adverse events are also to be reported to the reviewing IRB as per the IRB's reporting requirements. If required, adverse events will be reported to the appropriate regulatory agencies (e.g., Health Canada) according to all applicable laws and regulations. Specific instructions on notification procedures to AMO are included in **Appendix S**, Adverse Event Reporting.

Reporting of adverse events shall follow the Canadian Medical Devices Regulations concerning mandatory problem reporting (sections 59 through 61.1(2). For sites located outside the USA, reporting of adverse events shall follow ISO 14155 and country-specific guidelines, of which the shortest/strictest timeline requirement for reporting adverse events will be followed. General guidelines are provided below:

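### Appendix S describes a serious event more narrowly than the six criteria in Section 11.1, so a site following it could report some serious adverse events late or as non-serious

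*Protocol*

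**What the plan says.** Protocol Section 11.1, under Serious Adverse Event, lists six criteria, any one of which makes an event serious, whether or not it is related to the device. The first is that the event "is sight- or life-threatening". The others include that it "results in death", "requires inpatient hospitalization or prolongation of hospitalization", "results in permanent impairment of a body structure or body function", or "necessitates medical or surgical intervention to prevent permanent impairment to a body structure or function, or" leads to a fetal or congenital outcome, which is the sixth.

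Section 11.3 requires notice to the sponsor within 48 hours of detection for any serious adverse event and for any device-related event. For the steps themselves it points to Appendix S: "Specific instructions on notification procedures to AMO are included in" that appendix.

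Appendix S sorts events into three routes. The 48-hour route begins "In the event of a serious event (i.e., life- or sight-threatening incident) whether or not related to the device", and it also takes in device deficiencies that may have led to a serious event. The general route begins "For events that are not considered serious or related to the study device" and asks for an entry on the visit case report form. The third route is for device-related events not considered serious and asks for a Detailed Adverse Event Form. The second and third routes ask for timely submission and set no hour limit.

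**The concern.** Two parts of one protocol give different scopes for the same expedited report. Because the parenthesis in Appendix S is introduced by *i.e.*, it reads as a statement of what a serious event is, not as an example. The appendix neither repeats the Section 11.1 criteria nor refers to them. Staff using it as their working instruction could conclude that an event which is neither life-threatening nor sight-threatening belongs to one of the routes without a time limit.

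At stake are the speed of notice to the sponsor, the recorded seriousness of the event and, for some events, whether the Medical Monitor sees it as a report for review. The update form in Section 11.5 is also tied to the serious and/or device-related class.

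**Working it through.** No sample size, power or error-rate figure is involved. The check is a comparison of texts and a count.

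**Step 1. Criteria in Section 11.1 against the description in Appendix S.**

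| Section 11.1 criterion | Named in Appendix S? |
|---|---|
| Sight- or life-threatening | Yes |
| Death | No, but can be read into life-threatening |
| Hospitalization, new or prolonged | No |
| Permanent impairment | No |
| Intervention to prevent permanent impairment | No |
| Fetal or congenital outcome | No |

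Named: 1 of 6. Not named: 6 − 1 = 5. If death is taken as covered: 5 − 1 = 4 outside the wording.

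**Step 2. The time limit.** Section 11.3 and Appendix S both give 48 hours. The conflict is over which events the limit covers, not over its length.

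**Step 3. Where an event goes.** Take an event that meets only one of the four uncovered criteria.

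- Judged not device-related: Section 11.3 requires 48-hour notice because it is a serious adverse event. Read literally, Appendix S sends it to the visit case report form.
- Judged device-related: Section 11.3 requires 48-hour notice on both grounds. Read literally, Appendix S sends it to the Detailed Adverse Event Form with no hour limit.

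**Step 4. Medical Monitor.** Section 15.3 has the Medical Monitor review reports of serious and/or device-related events. Section 11.4 counts definitely, probably and possibly related events as device-related. A device-related event treated as non-serious therefore loses the 48-hour step but stays within the Medical Monitor's remit. An event leaves that remit only if it is serious solely on an uncovered criterion and is also judged unlikely to be related, or not related, to the device. Section 11.4 assesses device and procedure relatedness separately, so an event attributed to the surgery but not to the device could fall in this group.

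**Step 5. Device deficiencies.** Section 11.3 sets a 48-hour limit for any deficiency that could have led to a serious adverse event, and Section 15.3 has the Medical Monitor review these. In Appendix S the deficiency trigger sits in the same sentence as the parenthesis and inherits its narrower meaning.

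**The case against.** The strongest reply is that the duty is intact. Section 11.3 requires 48-hour notice of any serious adverse event without restriction, and it refers to Appendix S for procedure, not for the definition. The relevant Appendix S heading uses the term that Section 11.1 defines. A site would have to read the appendix in isolation to go wrong. There are also safeguards: all adverse events go on the case report form (Section 11.3), the listed anticipated ocular events must be reported (Section 11.1), the sponsor reviews adverse event listings (Section 15.1), and monitors check files for timely reporting (Section 15.2). All of this stands. It makes lasting miscoding less likely, but it does not secure notice within 48 hours, and the two texts still disagree.

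It is also fair that counting criteria overstates the practical gap. For ocular events, permanent impairment and intervention to prevent it overlap with sight-threatening events. Fetal outcomes are remote, since subjects are at least 45 and pregnancy or intended pregnancy is excluded. The gap is smaller than 4 of 6 suggests, but it is not empty: a hospitalization that threatens neither life nor sight is a plain example.

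Two stronger readings are tempting and are not supported.

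- *Flap complications would be missed.* Section 17 places flap complications among the vision-threatening risks, so they plausibly fall within the Appendix S wording. Section 10.7 also requires advance notice to the sponsor of non-refractive retreatments, including flap procedures.
- *The safety endpoint would fall by a known amount.* With 34 eyes per group, one eye is 1/34 = 2.9 percentage points, and a reader might take this as the bias per miscoded event. But the endpoint counts only non-flap-related events (Protocol Section 20.2; SAP Section 3.5), so miscoding a flap event cannot change it. For other events the figure is just the weight of one eye. The documents give no rate of misclassification from which to size an effect.

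**Conclusion.** The inconsistency is real. Appendix S names 1 of the 6 criteria, and 4 remain outside its wording if death is read as life-threatening. A site that follows it could report an event meeting only one of those four late, or record it as non-serious. The Section 11.3 duty remains, so this is a risk of delay and misclassification, not a removed obligation. For adverse events, the Medical Monitor's review is at risk only for those judged not even possibly device-related. The narrower wording also reaches device deficiencies.

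The conclusion rests on reading *i.e.* as defining and on some site staff using Appendix S as their working instruction. How often that would happen cannot be estimated from the documents. The point should be corrected because an operative safety instruction contradicts the protocol's own definition and the remedy is very small.

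**What to change.** Reconcile Appendix S with Sections 11.1 and 11.3. In Appendix S, replace the parenthesis after *serious event* with: *(any event meeting one or more SAE criteria in Section 11.1)*. Because the deficiency trigger is in the same sentence, this corrects it too. Repeating the six criteria in the appendix is optional; it helps staff who work from that page but creates a second list to keep aligned.

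The cost is one line in the next protocol version and a note to sites. It adds no reports beyond those Section 11.3 already requires and changes no analysis, sample size or clinical procedure. A separate mismatch would remain: Section 11.3 sets 48 hours for device-related events, while Appendix S sets no hour limit for the non-serious ones. That can be reconciled in the same edit.
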